9.8. Safety Analyses

All safety analyses will be performed on the SS.

9.8.1. Adverse Events

A summary of TEAEs that occur including the number of events reported, the number and percentage of subjects reporting at least 1 AE, the number and percentage of subjects discontinuing due to an AE, the number and percentage of subjects with at least 1 serious adverse event, and the number and percentage of deaths will be presented.

A breakdown of the number and percentage of subjects reporting each TEAE will be presented, categorized by SOC and PT coded according to the MedDRA dictionary. Note that counting will be by subject, not event, and subjects are only counted once within each SOC or PT.

A further tabulation of these data will be presented for TEAEs that are related to study drug, as defined by those AEs with relationship to study drug recorded on the eCRF as Possible or Probable. Events that are unrelated or remotely/Unlikely related will not be considered “related” for the Causality assessment. An AE with a missing relationship will be considered as having a relationship to study drug of possible. Subjects with multiple events within a particular SOC or PT will be counted under the category of their most drug-related event within that SOC or PT.

A summary of events reported, categorized by severity (mild, moderate, severe) will also be provided. AEs with missing or unknown severity will be considered severe. Subjects with multiple events within a particular SOC or PT will be counted under the category of their most severe event within that SOC or PT.

A summary of adverse events leading to discontinuation will be provided, grouped by system organ class and preferred term.

All AEs (including non-treatment-emergent events) recorded on the eCRF will be listed along with other information such as duration, severity, action taken, and perceived relationship to study drug.

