2.0 OBJECTIVES AND ENDPOINTS

2.1 Objectives

2.1.1 Primary Objective

The primary objective of this study is to evaluate the safety and tolerability of tozadenant in levodopa-treated PD patients experiencing motor fluctuations, based on assessment of TEAEs, vital signs, electrocardiograms (ECGs), and clinical laboratory tests.

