3.0 STUDY DESIGN

3.1 Study Description

This is a Phase 3, international, multicenter, open-label study in levodopa-treated patients with PD experiencing end-of-dose "wearing-off". This study includes a Screening Period of up to 6 weeks that starts with a Screening Visit, followed by a 52-week Open-Label Treatment Period and a Safety Follow-Up Visit 4 weeks after completion of investigational treatment. After providing written informed consent, patients will undergo screening evaluations. Patients must meet all inclusion criteria and none of the exclusion criteria and they must successfully complete the diary training and achieve 80% overall diary concordance with the PD diary trainer/rater including at least 1 OFF interval to be considered for randomization. If preliminary eligibility is confirmed by the investigator, patients will then be scheduled for a Baseline Visit and will be required to return a valid set of Baseline diaries. Final eligibility will be determined at the Baseline Visit.

Patients will return to the study site for evaluation at scheduled visits at Weeks 2, 6, 12, 24, 36 and 52. Patients will be contacted by telephone before the start of each 3-day PD diary completion period to be reminded to complete the diary. **Patients will also be scheduled for a laboratory draw (hematology measurement only) at Weeks 4, 8, 10, 16, 20 and 44.** A final Safety Follow-Up Visit (Week 56) will occur 28 ± 3 days after the patient's last open-label dose of tozadenant. Upon starting study treatment, patients will receive open-label tozadenant at a dose of 120 mg BID. Adjustments to the open-label tozadenant dose are allowed to be made by the investigator starting at Week 2 and at any of the subsequent visits. Doses of 60 or 120 mg

BID are permitted; the investigator may adjust a patient's dose to either level as clinically indicated. The Interactive Response System (IXRS) will be used to assign, track and manage the tozadenant inventory at each study site.

Patients' concomitant anti-PD medications may be adjusted as needed under the investigator's supervision (see [Section 5.9.1](#)). The optimal dose of open-label tozadenant for each patient will be defined following discussion between the patient and the investigator, taking into account the potential for improvement of disease symptoms and the tolerability profile.

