3. STUDY DESIGN

This is a Phase 3, international, multicenter, open-label study in levodopa-treated patients with PD experiencing end-of-dose “wearing-off”. This study includes a Screening Period of up to 6 weeks that starts with a Screening Visit, followed by a 52-week Open-Label Treatment Period and a Safety Follow-Up Visit 4 weeks after completion of investigational treatment. After providing written informed consent, patients will undergo screening evaluations. Patients must meet all inclusion criteria and none of the exclusion criteria and they must successfully complete the diary training and achieve 80% overall diary concordance with the PD diary trainer/rater including at least 1 OFF interval to be considered for enrollment. If preliminary eligibility is confirmed by the investigator, patients will then be scheduled for a Baseline Visit and will be required to return a valid set of Baseline diaries. Final eligibility will be determined at the Baseline Visit.

Patients will return to the study site for evaluation at scheduled visits at Weeks 2, 6, 12, 24, 36, and 52. Patients will be contacted by telephone before the start of each 3-day PD diary completion period to be reminded to complete the diary. A final Safety Follow-Up Visit (Week 56) will occur 28 ± 3 days after the patient’s last open-label dose of tozadenant. Upon starting study treatment, patients will receive open-label tozadenant at a dose of 120 mg BID. Adjustments to the open-label tozadenant dose are allowed to be made by the investigator starting at Week 2 and at any of the subsequent visits. Doses of 60 or 120 mg BID are permitted; the investigator may adjust a patient’s dose to either level as clinically indicated. The Interactive Response System (IXRS) will be used to assign, track and manage the tozadenant inventory at each study site.

The Schedule of Events/Evaluations for is shown below in [Table 1](#).

Table 1: Schedule of Events/Evaluations

Assessments	Study Period	Baseline	Open-Label Treatment						Safety	Early	Unscheduled
	Screening ^a	Predose	(52 weeks)						Follow-Up	Termination ^w	
	Study Week ^b	BL	2	6	12	24	36	52	56		
Study Visit	-6 to -1		(± 3 d)	(± 3 d)	(± 3 d)	(± 7 d)	(± 7 d)	(± 14 d) [16 weeks]	(28 ± 3 d after last dose of IMP)		
	V1	V2	V3	V4	V5	V6	V7	V8	V9		
Written Informed Consent	X										
Demographics and Medical History, including neurological and PD history	X										
Recording of concomitant and anti-PD medications	X	X	X	X	X	X	X	X	X	X	X

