5. DEFINITIONS

5.1. Treatment Group Labels

The following treatment group label will be used in the TFLs:

- Tozadenant

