9.3. Treatments

9.3.1. Extent of Study Drug Exposure

The number of days of exposure to study drug and average daily dose (mg/day) will be summarized by study visit in the SS. Average daily dose will be calculated as (number of tablets dispensed minus the number of tablets returned minus the number of tablets lost) divided by number of days from visit i-1 to visit i and multiplied by the mg of the tablets. The proportion of subjects who took 60mg, 120mg will be summarized by study visit in the SS. Subjects who took only 60mg doses from visit i-1 to visit i will be included in the numerator for the 60mg category for visit i; subjects who took only 120mg doses from visit i-1 to visit i will be included in the numerator for the 120mg category for visit i. Descriptive statistics for the total number of tablets dispensed, number of tablets returned and number of tablets lost will be displayed by study visit and overall. Compliance with study drug will be calculated as (number of tablets dispensed minus the number of tablets returned minus the number of tablets lost) divided by the scheduled number of doses, expressed as a percentage. If this percentage is calculated greater than 100%, then compliance will be calculated 1 minus (the calculated percentage minus 1). Compliance will be summarized overall and by scheduled weeks for the safety analysis set.

Study drug dispense and accountability with the reason for not returning tablets is captured on the CRF and will be presented in the data listings.

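### No planned table gives TEAEs leading to dose reduction, or how many patients were ever reduced from the 120 mg BID start

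*SAP*

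**What the plan says.** **Objective.** Protocol 2.1.1: "The primary objective of this study is to evaluate the safety and tolerability of tozadenant". The sentence goes on to name TEAEs, vital signs, ECGs and laboratory tests as the basis.

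**Dosing.** SAP 3: "Upon starting study treatment, patients will receive open-label tozadenant at a dose of 120 mg BID". Changes are allowed from Week 2: "Doses of 60 or 120 mg BID are permitted; the investigator may adjust a patient’s dose to either level as clinically indicated". Protocol 3.1 says the patient and investigator settle the dose by "taking into account the potential for improvement of disease symptoms and the tolerability profile". The dosing table in Protocol 5.6 has a row for a reduced dose and a row for a later increase.

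**Adverse event tables.** SAP 9.8.1 plans an overview and tables of all TEAEs, drug-related TEAEs and TEAEs by severity. SAP 9.8.2 adds serious TEAEs. All are on the Safety Set. For action on study drug, the overview counts patients who discontinued because of an adverse event, and then: "A summary of adverse events leading to discontinuation will be provided, grouped by system organ class and preferred term". The listing carries "other information such as duration, severity, action taken, and perceived relationship to study drug".

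**Dose and labels.** SAP 9.3.1: "The proportion of subjects who took 60mg, 120mg will be summarized by study visit in the SS". A patient counts at a dose level for a visit only if that was the sole dose taken since the previous visit. SAP 5.1 states "The following treatment group label will be used in the TFLs" and gives one label, Tozadenant, with no split by dose.

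**The concern.** Under flexible dosing, a patient who does poorly on the starting dose can either stop treatment or step down and stay in. The plan tabulates the first outcome and not the second. A patient who steps down because of a TEAE contributes that event to the general TEAE tables, but no adverse event table identifies the patient as having needed a lower dose.

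Tolerability is part of the primary objective and everyone starts on the same dose. A reader of the study report will therefore look to the discontinuation row as the main summary of tolerability. The more patients are kept in the study by stepping down, the lower that row will be, and nothing beside it shows how many were kept in that way.

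**Working it through.** **1. The plan's own figures.** Neither document states an expected rate of discontinuation or of dose reduction. The only planning figure is the number screened: 450 / (1 − 0.30) = 643, which agrees with the stated approximate 645. It does not bear on this point beyond supplying N = 450.

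**2. Which outputs could show an adverse-event-driven reduction?**

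| Output | Reduced patient included? | Reduction shown? | Cause shown? |
|---|---|---|---|
| All, related, severity-graded and serious TEAE tables (SAP 9.8.1, 9.8.2) | Yes | No | No |
| Discontinuation count and table (SAP 9.8.1) | Only if the patient later discontinues for an adverse event | No | No |
| Adverse event listing (SAP 9.8.1) | Yes | Possibly, through action taken | Possibly, event by event |
| Dose level by visit (SAP 9.3.1) | Yes, if only 60 mg was taken in the interval | Per visit only | No |
| Average daily dose (SAP 9.3.1) | Yes | Mixed with missed tablets | No |

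**3. Why the by-visit dose split does not give the number ever reduced.**

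- *It is not cumulative.* Suppose 45 of 450 patients are on 60 mg at one visit and 45 of 450 at a later one. The number ever reduced across those two visits lies between 45 (the same patients, 10%) and 45 + 45 = 90 (different patients, 20%). Re-escalation is allowed, so both are possible.
- *It omits mixed intervals.* A patient who took both doses between two visits falls in neither category. Protocol 6.2.21.2 allows dispensing at an unscheduled visit, so a change within an interval can occur. A patient who changes that way and then leaves may never appear at 60 mg.
- *It loses leavers.* SAP 11.1 (item 12) sets the default denominator to patients with an observation, so those who have left drop out of later visits.
- *It has no link to adverse events.*

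**4. Illustration of size.** The rates here are assumed. The two groups are taken as non-overlapping, and intervals are exact 95% with N = 450.

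Combined rate = (discontinued for an adverse event + reduced for an adverse event and retained) / 450.

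Discontinuation only, at an assumed 10%: 45/450 = 10.0% (7.4% to 13.2%).

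| Assumed reduction | Combined count | Combined rate (95% CI) | Ratio to 10.0% |
|---|---|---|---|
| 5% | 45 + 22 = 67 | 14.9% (11.7% to 18.5%) | 1.5 |
| 10% | 45 + 45 = 90 | 20.0% (16.4% to 24.0%) | 2.0 |
| 20% | 45 + 90 = 135 | 30.0% (25.8% to 34.5%) | 3.0 |
| 30% | 45 + 135 = 180 | 40.0% (35.4% to 44.7%) | 4.0 |

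If discontinuation is varied from 5% (22/450 = 4.9%) to 15% (68/450 = 15.1%), and reduction from 5% to 30%, the combined rate runs from (22 + 22)/450 = 9.8% to (68 + 135)/450 = 45.1%. The ratios restate the assumed inputs. They are not estimates for this trial.

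**The case against.** **The plan follows the protocol.** Protocol 11.5 names TEAEs, serious and nonserious, and TEAEs causing permanent withdrawal as the primary safety variables, and SAP 9.8.1 delivers these. The objective concerns tozadenant as flexibly dosed, not the 120 mg BID start alone, and one pooled label fits that. This stands. The plan has not failed its protocol, and what is proposed is an addition.

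**Reduced patients are not lost.** A reader might infer that only discontinuation-related events are tabulated, or that reduced patients count in no tolerability result. The documents do not support that. Every TEAE table is on the Safety Set and includes these patients and their events, and the 60 mg share by visit gives an indirect view of reductions. Nor does any table label a patient as having tolerated the drug or report an intolerance rate.

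**Not every reduction is intolerance.** Tolerability is one of two stated considerations. This stands, and it is why the added table should rest on adverse events recorded as leading to reduction, not on dose changes alone.

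**Intolerance may already end in discontinuation.** The synopsis, under its discontinuation criteria, says patients with drug-related TEAEs that they do not tolerate leave the study. Read literally, the discontinuation table would capture those patients. But Protocol 4.3.1 lists intolerable adverse events among matters to discuss with the Medical Monitor that could end in discontinuation, and Protocol 3.1 and 5.6 provide for a lower dose with tolerability in view. These passages do not agree, so discontinuation cannot be assumed to capture every such patient.

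**The data may not exist.** Neither document shows a collected field for the reason for a dose change, and the codes of the action-taken field are not given. This stands and limits the fix.

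**Conclusion.** The concern holds in a limited form. Discontinuation is the only study-drug action tabulated for adverse events. TEAEs leading to dose reduction, and the number of patients ever reduced, cannot be read from any planned table. Discontinuation alone may therefore understate how often the 120 mg BID start was not tolerated.

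The size is unknown. The range of about 15% to 40% against 10% rests wholly on assumed rates and on the two groups not overlapping. A reader might infer from it that intolerance is understated 2- to 4-fold. That does not follow: with 5% reduced the ratio is 1.5, and the plan never claims to report an intolerance rate. Nor do the documents support saying that the primary objective cannot be met, since the TEAE, vital sign, ECG and laboratory summaries it rests on are all planned.

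This is a gap in descriptive reporting that should be closed before the tables are finalised. It is not an error in an existing analysis.

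**What to change.** In SAP 9.8.1 add, on the Safety Set:

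1. TEAEs leading to dose reduction, by system organ class and preferred term, from the action-taken field, after confirming that its codes include dose reduction.
2. The number (%) of patients ever reduced to 60 mg BID and the number (%) re-escalated, from the assigned-dose records (Protocol 5.11 has the IXRS dispense according to the dose level the investigator assigns).
3. A combined row, number (%) with a TEAE leading to dose reduction or discontinuation, counting each patient once and shown beside the discontinuation row.

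Label all three as descriptive. Report a reason for reduction only where an adverse event's action taken records it, because no other source for the reason is shown.

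Separately, the discontinuation criteria in the synopsis should be reconciled with Protocol 3.1, 4.3.1 and 5.6 on what follows when a drug-related TEAE is not tolerated. Which reading applies is for the sponsor to decide. It affects how the discontinuation table can be interpreted.

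The cost is a few extra descriptive tables and a tolerability figure that may look less favourable. SAP 9 plans no formal tests, so there is no inferential cost, and no dosing rule changes.

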9.8.2. Deaths and Serious Adverse Events

Serious TEAEs will be summarized by the number and percentage of subjects reporting each AE, categorized by SOC and PT coded according to the MedDRA dictionary. Note that counting will be by subject, not event, and subjects are only counted once within each SOC or PT.

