11. **Patients with an absolute neutrophil count less than 1000/mm³ (or 1.0 x 10E9/L).*** **Following study drug discontinuation, these patients will require weekly hematology measurement until the WBC and/or ANC returns to 75% of the baseline value (Visit 2). Assess for adverse events and concomitant medication changes and record as an unscheduled visit. Discuss with medical monitor to assure that the patient is discontinued from study drug and that the appropriate follow up safety measures are taken.**

*Any patient experiencing a decline in absolute neutrophil count (ANC) and/or white blood cells (WBC) by 50% from baseline (Visit 2) will require weekly hematology measurement until the WBC and/or ANC returns to 75% of the baseline value. The patient will continue with dosing during the weekly hematology follow-up. Assess for adverse events and concomitant medication changes and record as an unscheduled visit. If the WBC and/or ANC returns to 75% of baseline, the patient should return to routine evaluations as outlined in the Schedule of Events/Evaluations. Discuss with medical monitor.

All patients who discontinue prematurely from the study will be requested to return to the study site as soon as possible to complete the safety and efficacy evaluations outlined for an Early Termination Visit in the Schedule of Events/Evaluations (Table 1) and in Section 6.2.20. The Early Termination Visit should be done under IMP treatment, if possible. After Early Termination, the patient will also be asked to return for a Safety Follow-Up Visit to be scheduled 28 (\pm 3) days after their last dose of IMP, unless the Early Termination Visit itself occurred 28 or more days after the last dose of IMP (see Section 6.2.19).

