9.2.2 Procedures for Reporting Serious Adverse Events

If an SAE is reported, the Sponsor must be informed within 24 hours of receipt of this information by the site. The SAE Report Form must be sent to:

- [REDACTED]
- [REDACTED]
- [REDACTED]
- [REDACTED]
- [REDACTED]
- [REDACTED]

The email address, fax and telephone number used for SAE reporting is also provided on the SAE/ Pregnancy Reporting Form Cover Page, along with Sponsor contact information. An SAE Report Form will be provided to the investigator. The SAE Report Form must be completed in English.

The investigator must forward to the Sponsor (or its representative) a duly completed SAE Report Form provided by the Sponsor, even if the data are incomplete, or if it is obvious that more data will be needed in order to draw any conclusions. Information recorded on this form will be entered into the global safety database.

It is important for the investigator, when completing the SAE Report Form, to include the assessment as to a causal relationship between the SAE and the IMP administration. This insight from the investigator is very important for the Sponsor to consider in assessing the safety of the IMP and in determining whether the SAE requires reporting to the regulatory authorities in an expedited manner.

Additional information (e.g., autopsy or laboratory reports) received by the investigator must be provided within 24 hours. All documents in the local language must be accompanied by a translation in English, or the relevant information included in the same document must be summarized in the SAE Report Form.

The investigator is specifically requested to collect and report to the Sponsor (or its representative) any SAEs (even if the investigator is certain that they are in no way associated with the IMP) up to 4 weeks from the date of last IMP for each patient, and to also inform participating patients of the need to inform the investigator of any SAE within this period. Serious AEs that the investigator thinks may be associated with the IMP must be reported to the Sponsor regardless of the time between the event and the end of the study.

Upon receipt of the SAE Report Form, the Sponsor will perform an assessment of expectedness of the reported SAE. The assessment of the expectedness of the SAE is based on the current IB.

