5.12. Treatment-Emergent Adverse Events (TEAEs)

TEAEs are AEs which first occur or increase in severity or relationship to study drug after the first dose of IMP through the Safety Follow-up. Should the day of the AE be “unknown” and the AE in question occurs in the same month or a following month as the date of first dose, the AE will be considered treatment emergent. Should the month of the AE be “unknown” and the AE in question occurs in the same year or a following year as the date of first dose, the AE will be considered treatment emergent. Should the start date be missing then the AE will be considered treatment emergent.

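### SAP 9.8.1 and 9.8.2 count serious events and deaths only as TEAEs, so a fully dated serious or fatal event starting after the Safety Follow-Up is required data that enters no planned count

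*SAP*

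**What the plan says.** **Window.** SAP 5.12 defines a TEAE as an event that first occurs, or gets worse in severity or in attributed relationship, "after the first dose of IMP through the Safety Follow-up". Protocol 3.1 places that visit: "A final Safety Follow-Up Visit (Week 56) will occur 28 ± 3 days after" the last open-label dose.

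**Counts.** SAP 9.8.1 opens with "A summary of TEAEs that occur including the number of events reported". The same sentence goes on to subjects with a serious event "and the number and percentage of deaths will be presented". The table of drug-related events in that section is also restricted to TEAEs. SAP 9.8.2 plans one table: "Serious TEAEs will be summarized by the number and percentage of subjects reporting each AE". It describes no table of deaths, although its heading names them.

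**Required data.** Protocol 9.2.2 has the investigator report serious events of any cause "up to 4 weeks from the date of last IMP for each patient". Those that the investigator thinks may be associated with the drug "must be reported to the Sponsor regardless of the time between the event and the end of the study".

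**What covers later events.** SAP 9.8.1 lists all adverse events recorded on the eCRF, including those that are not treatment-emergent. Protocol 9.2.3 directs serious-event information obtained after database lock to the global safety database.

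**The concern.** The reporting duty in the protocol runs longer than the counting window in the SAP, and no other planned count bridges the two. Beyond 4 weeks after the last dose, the only serious events that must be reported are those the investigator links to the drug. So the uncounted late cases are, by construction, mostly the drug-attributed ones.

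The primary objective is safety and tolerability. The number of deaths and the number of patients with a serious event are among the first figures a reader will look for. Under the SAP as written, both can be lower than what the sponsor has been told, and the tables would not show it.

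**Working it through.** This is mainly a comparison of definitions. The arithmetic only sets the window and the weight of one event.

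**The plan's own figure.** The only planning number is the screening target (SAP 3.2, Protocol 11.9). With 30% screen failure, 450 / (1 − 0.30) = 642.9, so 643, against a stated figure of approximately 645. It reproduces. The point does not depend on it except for the 450.

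**Window in days since last dose.**
- Safety Follow-Up: 28 − 3 = day 25 to 28 + 3 = day 31 (Protocol 3.1).
- Serious events of any cause: required through 4 × 7 = day 28 (Protocol 9.2.2).
- Largest all-cause gap: 28 − 25 = 3 days, namely days 26, 27 and 28 after a day-25 visit. With a visit on day 28 or later there is no all-cause gap.
- Serious events thought related: required with no end date, so the gap runs from the visit onward.

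**Cases against the rules.**

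| Event | Required by Protocol 9.2.2 | TEAE under SAP 5.12 | Counted in SAP 9.8.1 / 9.8.2 |
|---|---|---|---|
| Starts before the visit, patient dies after it | Yes | Yes | Can be counted |
| Serious, any cause, starts day 26–28 after a day-25 visit | Yes | No | No |
| Serious or fatal, thought related, starts after the visit | Yes | No | No |
| Serious, thought unrelated, starts after the visit and after 4 weeks | No | No | No |

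Rows two and three are the gap. Row one is outside it because SAP 5.12 works on when an event begins or worsens, not on the date of its outcome.

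**Two edge cases.**
- SAP 5.12 puts an event with an unknown start day into the TEAE set if its month is that of the first dose or any later month, with no upper limit. A late event with an incomplete date is therefore counted while the same event with a full date is not. That is why the point is confined to fully dated events.
- A patient whose Early Termination Visit falls 28 or more days after the last dose needs no Safety Follow-Up Visit (Protocol 6.2.20). For that patient SAP 5.12 gives no end to the window.

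**Weight of one event.** If all 450 enrolled patients are dosed, so that the Safety Set is 450:
- one uncounted patient: 1/450 = 0.22 percentage points;
- two: 2/450 = 0.44 percentage points.

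The documents give no rate of late events, so no total can be calculated. SAP section 9 plans descriptive summaries without tests, and these tables carry no confidence intervals, so none are given here.

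**The case against.** The strongest reply is that a treatment-emergent cut-off is normal practice, and that this one ends close to where the protocol stops collecting serious events of every cause. The open-ended sentence in Protocol 9.2.2 is a duty to report to the sponsor, and the form feeds the safety database; it does not say that late cases belong in the clinical tables. Protocol 9.1.8 already provides for ongoing reconciliation of serious events, the eCRF listing would show a late event recorded there, and Protocol 11.5 speaks of presenting all adverse events. A table of all serious events to database lock would also mix complete early reporting with late reporting selected by causality.

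Much of this stands. The cut-off is not an error and should stay. The selection of late events is real and limits how they may be shown. But a listing gives no number, and an event held only in the safety database does not reach it. The wider wording of Protocol 11.5 is not carried into any SAP table.

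Two stronger readings are tempting, and the documents do not support them.
- A reader might infer that every death after the Safety Follow-Up is lost. It is not: a death from an event that began in the window is the outcome of a TEAE, and nothing in SAP 9.8.1 excludes it.
- A reader might infer that the consequences of a neutrophil fall escape the counts, because Protocol 4.3.2 says "these patients will require weekly hematology measurement until the WBC and/or ANC returns to 75% of the baseline value" after stopping. The fall that triggers stopping arises on treatment. Clinically significant laboratory abnormalities are recorded as adverse events (Protocol 11.5), and blood dyscrasias are an example of an important medical event (Protocol 9.2.1), so it would normally be a TEAE. The weekly checks are unscheduled visits, which Protocol 6.2.21 places before the Safety Follow-Up. Only a separate event with later onset could be missed.

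**Conclusion.** The point holds in a limited form. A serious or fatal event with a known onset after the Safety Follow-Up enters no planned death, serious-event or related-event count when it is thought related to the drug, or when it is of any cause and falls on days 26 to 28 after a day-25 visit. It appears at most in the eCRF listing, although Protocol 9.2.2 requires it.

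The number of such events is unknown and may be zero. Each one is worth 0.22 percentage points, assuming all 450 enrolled patients receive a dose. No hypothesis test is affected, and no conclusion is shown to change. The change is still worth making: the undercount follows from a stated rule, it concerns deaths and drug-attributed serious events in a study whose primary objective is safety, and it is cheap to correct.

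**What to change.** Keep the TEAE definition and the TEAE tables. Then:

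1. In SAP 9.8.1, state that the death count covers all deaths known to have occurred after first dose in the Safety Set, up to database lock.
2. In SAP 9.8.2, add one table of all deaths and serious events with onset after first dose, split into through and after the Safety Follow-Up. Where no such visit takes place, split at 4 weeks after the last dose. Show relationship to drug and days since last dose.
3. Base that table on serious events reconciled with the safety database before lock.
4. Give the post-window serious events as counts only, apart from the TEAE percentages, with a note that after 4 weeks only those thought related must be reported.

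The cost is some SAP wording and one extra table; nothing changes in study conduct. The drawback is that late ascertainment of unrelated events stays incomplete. The split and the note make this visible but do not cure it.
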